2.0 (Dec 23, 2020)	
As per discussion between sponsor and BPSI/BPSUSA, the following sections were revised from the previously approved protocol:
 
 i) Protocol Title Pages and Headers – Protocol Version and Date revised to Version 2.0 and Dec 23, 2020, respectively. ii) Updated BPSUSA telephone and fax number. Following sections have been updated: 
 • Title page • Section SPONSOR, INVESTIGATORS AND FACILITIES • Section INVESTIGATOR CREDENTIALS iii) Section Table of Contents – updated pagination iv) Tuberculosis (TB) Test and/or Questionnaire have been removed from the study. Following sections have been updated: 
 • Section 2.0 TABLE OF STUDY PROCEDURES • Section 5.1.1 Screening (Visit 1) • Section 7.3 Exclusion Criteria • Section 8.6 Tuberculin Test (has been deleted) • APPENDIX A – SCHEDULE OF EVENTS v) Included light smokers to this study and removed cotinine test. Following sections have been updated: 
 • Section 1.0 SYNOPSIS • Section 2.0 TABLE OF STUDY PROCEDURES • Section 4.1 Study Objective • Section 5.0 STUDY DESIGN • Section 6.0 STUDY POPULATION • Section 7.0 SUBJECT SELECTION AND WITHDRAWAL/TERMINATION • APPENDIX A – SCHEDULE OF EVENTS

-
- APPENDIX B – CLINICAL LABORATORY ASSESSMENT
- vi) The test for SARS-CoV-2 at screening has been removed, and the test at check-in will be done if applicable, related wordings have been updated. Following sections have been updated:
- Section 1.0 SYNOPSIS
 - Section 2.0 TABLE OF STUDY PROCEDURES
 - Section 8.5.5 SARS-CoV-2 Test
 - APPENDIX A – SCHEDULE OF EVENTS
- vii) Section SPONSOR, INVESTIGATORS AND FACILITIES has been updated for the IRB official name.
- viii) Section 7.3 Exclusion Criteria has been updated regarding Systolic blood pressure and temperature normal range, timeframe for the restriction of beverages containing grapefruit and/or pomelo consumption.
- ix) Section 7.5 Study Restrictions has been updated regarding timeframe for the restriction of beverages containing grapefruit and/or pomelo consumption.
- x) Section 8.5.4 Pulse Oximetry and Respiratory Rate has been updated to add normal range.
- xi) Section 8.6 Vital Signs has been updated regarding vital sign normal ranges.
- xii) End-of-Study (EOS) now has one-week ± 3 days window. Following sections have been updated:
- Section 2.0 TABLE OF STUDY PROCEDURES
 - Section 5.1.3 Post-Study [End-of-Study (EOS)]/Early Termination
- xiii) Section 8.5.3 Temperature Check. Temperature will be measured using an oral thermometer instead of a non-contact thermometer.
- xiv) Section 9.3 Drug Inventory has been updated regarding the purchase of study drug.
- xv) Section 11.1.1 Treatment-emergent adverse events (TEAEs) added sentence “**The PI/sub-I will be responsible for determining whether a TEAE is possibly related to the SARS-CoV-2 and document accordingly.**”
-

- xvi) Section 11.3 Adverse Events and Serious Adverse Events Reporting has been updated regarding the responsibility of notifying the local IRB or regulatory agency and SAE contact.
- xvii) In Section 13.1 Safety Data Set, related sentences have been updated to: “In a case where SARS-CoV-2 related TEAEs lead to the withdrawal **or dismissal** of approximately 5 % or more of the dosed subjects, a subgroup analysis **related to Adverse Events (AE)** may be performed. **And the safety listings and tables for AE with subgroup and the total safety population will both be presented.**”
- xviii) Section 13.2.2 Statistical Analysis of Pharmacokinetic Data, updated statistical model regarding dosing in groups.
- xix) In Section 15.3 Study Completion/Termination, related sentences have been updated to “BioPharma Services USA Inc. and/or the Sponsor reserve the right to terminate the study at any time, ~~and~~ for any reason **related to the safety of subjects or due to any other non-study specific reason.**”
- xx) Minor administrative/grammatical revisions were also made.

The study ICF was also revised to reflect applicable changes.

3.0 (Jun 22,
2021)

As per discussion between sponsor and BPSI/BPSUSA, the following sections were revised from the previously approved protocol:

- i) *Protocol Title Pages and Headers* – Protocol Version and Date revised to Version 3.0 and Jun 22, 2021, respectively.
- ii) Non or light smoking has been removed from Section 1.0. 4.1, 5.1.2.2 and 6.0.
- iii) Confinement has been updated to read as: “From at least 12 hours prior to dosing until at least 72 hours post dose, for a total of approximately 84 hours for each study period.” And Footer in Section 2.0 and 5.2 has been revised accordingly.
- iv) Additional measurements of the heart rate and blood pressure have been added at 48- and 72-hour post-dose for

additional safety monitoring. Therefore, Sections 1.0, 2.0, 8.6 and Appendix A have been updated.

1.0 SYNOPSIS

Title:	A Single Dose, Open-Label, Randomized, Four-Way Crossover, Fully Replicate, Bioequivalence Study of Generic Tacrolimus Capsules and Prograf® Capsules in Healthy Volunteers under Fasting Conditions.
Objective:	The objective of this study is to investigate the bioequivalence of Tacrolimus 1 mg capsules [REDACTED] and Prograf® 1 mg capsules [REDACTED] in healthy male and non-pregnant, non-lactating female volunteers under fasting conditions.
Experimental Design:	A single-dose, randomized, open-label, fully replicate crossover, four-period, two-treatment, two-sequence, bioequivalence study.
Study Rationale:	This is an in-vivo study to investigate the bioequivalence of generic tacrolimus and its reference listed drug (RLD). The outcome of this study will help further the Agency's understanding about pharmacokinetic (PK) performance of tacrolimus in a healthy volunteer population and improve review standards for bioequivalence of narrow therapeutic index (NTI) drugs.
Study Population:	72 subjects, including 8 standbys, will be enrolled to ensure dosing of approximately 64 subjects. The subjects may be dosed in more than one cohort. Healthy male and non-pregnant, non-lactating female volunteers, 18 - 59 years of age, inclusive, with a body mass index (BMI) within 18.5-33.0 kg/m ² , inclusive.
Test Drug (T):	Tacrolimus 1 mg capsules [REDACTED]
Reference Drug (R):	Prograf® 1 mg capsules [REDACTED]
Treatment:	1 × 1 mg capsules in each study period
Duration of Confinement:	From at least 12 hours prior to dosing until at least 72 hours post-dose, for a total of approximately 84 hours for each study period.
Washout:	At least 14 days between each dosing.
Safety Monitoring:	
• Vital signs (blood pressure [BP] and heart rate [HR]) will be obtained at pre-dose and at 1, 2, 4, 6, 12, 24, 48 and 72 hours after dosing in each study period.• All tests in Appendix B at screening, and selected tests at each period check-in and post-study.• The PI/Sub-Investigator will be present from approximately 30 minutes prior to dosing until at least 4 hours after the last subject is dosed in each study period. The PI/Sub-Investigator will remain on-call throughout the duration of the study.
COVID-19 prevention and control:	
• Temperature, pulse oximetry and respiratory rate will be measured at screening, at each check-in, at pre-dose, at 6- and 12-hours post dose, then at every 12 hours until discharge at each study period, at return visits and at end of study (EOS) visit.

	
 • A COVID-19 symptom check and COVID-19 questionnaire will also be completed at screening, at each check-in, at return visits and at EOS visit. • If applicable, a locally available test for SARS-CoV-2 will be performed at each period check-in.
Type of Vacutainer	Pre-chilled K ₂ EDTA Vacutainer®, 4 mL
Blood Sampling Time points:	28 PK Timepoints: Pre-dose (0 hour) and at 0.25, 0.50, 0.75, 1.00, 1.25, 1.50, 1.75, 2.00, 2.25, 2.50, 2.75, 3.00, 3.50, 4.00, 5.00, 6.00, 8.00, 10.00, 12.00, 16.00, 24.00, 36.00, 48.00, 72.00, 96.00, 120.00 and 144.00 hours after study drug dosing in each study period.
Total Blood Volume:	Approximately 520 mL of blood, including blood samples for PK time points, pre- and post- study procedures and the selected laboratory testing at each study period.
Analyte(s) to be measured:	Whole blood samples will be assayed for tacrolimus using a validated analytical method according to the principles of Good Laboratory Practice.
Statistical Analysis:	The ln-transformed PK parameters AUC ₇₂ , AUC _t , AUC _{inf} and C _{max} will be analyzed using both an unscaled average bioequivalence procedure and a reference-scaled average bioequivalence procedure.
	
Determination of the Within-subject Standard Deviation of the Test and Reference Products (S_{WT} and S_{WR}) for the PK Parameters AUC₇₂, AUC_t, AUC_{inf} and C_{max}
 
Reference Scaled Average Bioequivalence Procedure
 
The 95% upper confidence bound for $(\mu_T - \mu_R)^2 - \theta S_{WR}^2$ will be determined for the ln-transformed PK parameters AUC₇₂, AUC_t, AUC_{inf} and C_{max} using a PROC MIXED model in SAS.
 
Unscaled Average Bioequivalence Procedure
 
The 90% Confidence Intervals (CI) for the Test/Reference ratios of geometric means for the PK parameters AUC₇₂, AUC_t, AUC_{inf} and C_{max} will be calculated using a PROC MIXED model in SAS.
 
T_{max}, Lambda and T_{1/2} will be analyzed using an un-scaled procedure.
 
Calculation of the 90% CI for the Ratio of the Within-subject Standard Deviation of Test Product to Reference Product ($\sigma_{WT} / \sigma_{WR}$)
 
The 90% confidence interval of the ratio of the within subject standard deviation of test product to reference product ($\sigma_{WT} / \sigma_{WR}$) will be calculated for tacrolimus.

Bioequivalence Criteria:	
To establish bioequivalence, all the following conditions for individual PK parameter(s) AUC₇₂ and C_{max} must be met:
 
 • The 90% CI for the Test/Reference ratios of geometric means are completely contained within 80.00%-125.00%.

- The 95% upper confidence bound for $(\mu_T - \mu_R)^2 - \theta S_{WR}^2$ should be less than or equal to 0.
- The upper limit of the 90% confidence interval for the Test/Reference ratio of the within-subject standard deviation ($\sigma_{WT} / \sigma_{WR}$) is less than or equal to 2.5.

2.0 TABLE OF STUDY PROCEDURES

Procedure/Activity	Time points						
	Visit 1	Visit 2 to 17					
	Screening	Each Period Check-in	Period 1	Period 2	Period 3	Period 4	Post-Study/ EOS [^]
Written informed consent	X						
Drugs of Abuse	X	X					
Alcohol Test	X	X					
Pregnancy (hCG) Test*	X	X					
Vital Signs (BP & HR)	X	X	X ^a	X ^a	X ^a	X ^a	X
Safety measures for COVID-19 [#] (Symptom Check, Temperature, Pulse Oximetry and RR)	X	X	X	X	X	X	X
SARS-CoV-2 Test ^c		X					
BMI	X						
Laboratory Testing ⁺ (Appendix B)	X	X					X
ECG	X						
Inclusion/Exclusion Assessment	X	X ^b					
Restrictions Compliance Check		X ^d	X ^d	X ^d	X ^d	X ^d	
Physical Exam	X						X
Tacrolimus Capsule Administration			X	X	X	X	
PK Sampling			X ^e	X ^e	X ^e	X ^e	
Adverse Event Reporting		X ^f	X ^f	X ^f	X ^f	X ^f	X

Meals		X ^g					
-------	--	----------------	----------------	----------------	----------------	----------------	--

- [^] EOS with one-week ±3 days window.
- ^{*} Serum pregnancy test at screening and urine pregnancy test at each period check-in.
- [#] Temperature, pulse oximetry and respiratory rate will be measured at screening, at each check-in, at pre-dose, at 6- and 12-hours post dose, then at every 12 hours until discharge at each study period, at return visits and at EOS visit. A COVID-19 symptom check, and COVID-19 questionnaire will also be completed at screening, at each check-in, at return visits and at EOS visit.
- [†] All tests in [Appendix B](#) at screening, and selected tests at each check-in and at EOS (details in [Appendix A](#) and [Appendix B](#)).
- ^{a-} Vital signs measurements (BP and HR) to be obtained at pre-dose and at 1, 2, 4, 6, 12, 24, 48 and 72 hours after dosing in each study period.
- ^b Only at check-in for the period 1.
- ^{c-} At each period check-in, if applicable.
- ^{d-} Confirmed at check-in and each return visits, if applicable.
- ^{e-} PK sampling: Pre-dose (0 hour) and at 0.25, 0.50, 0.75, 1.00, 1.25, 1.50, 1.75, 2.00, 2.25, 2.50, 2.75, 3.00, 3.50, 4.00, 5.00, 6.00, 8.00, 10.00, 12.00, 16.00, 24.00, 36.00, 48.00, 72.00, 96.00, 120.00 and 144.00 hours after study drug dosing in each study period. PK sampling at 96, 120 and 144 hours will be collected during outpatient return visits.
- ^{f-} Pre-dose conditions at Period 1 check-in and each return visit, if applicable. AEs will be monitored throughout the study.
- ^{g-} Meals will be served at the scheduled times during confinement prior to dosing and at approximately 4.5, 9.5, 13.5, 24.5, 28.5, 33.5, 37.5, 48.5, 52.5, 57.5 and 61.5 hours after dosing.

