5.1.2 Treatment Phase (Visit 2 to 14)

5.1.2.1 Study Period Check-in Procedures (Visit 2, 6, 10 and 14)

At check-in for each study period, subjects will be questioned about whether they have complied with the study restrictions and will be asked about the COVID-19 related questionnaire. Temperature, pulse oximetry and respiratory rate will be measured at each check-in and at pre-dose at each study period. Subjects will be asked to come to the study site approximately 24 hours prior to dosing and will be discharged after 72-hour blood draw.

If drug therapy other than that specified in the protocol was used, a decision to continue or discontinue the subject's participation will be made by the PI/Sub-Investigator and will be reported to the Sponsor.

Urine tests for drugs of abuse and a breath alcohol test will be performed on all subjects at each study period check-in. In addition, urine hCG testing will be performed on all female subjects at each study period check-in.

The subject's hemoglobin and hematocrit levels will be assessed by the PI/Sub-Investigator regarding the subject's continued participation. Male subjects having a hemoglobin level below 12.0 g/dL and/or hematocrit level below 36.0% or a female subjects having hemoglobin level below 12.0 g/dL and/or hematocrit level below 34.0%, the subjects will not be permitted to continue in the study unless deemed non-clinically significant (NCS) by PI/Sub-Investigator.

Clinical staff reserves the right to conduct random testing (urine drugs of abuse, urine hCG [females only], or alcohol) on any subject at any time during the study to ensure subject compliance and/or safety. Any subject with a positive test for urine drugs of abuse, alcohol or urine hCG (females only) will be dismissed immediately from the study.

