5.1.3 Post-Study [End-of-Study (EOS)]/Early Termination

Clinical laboratory tests (hematology, serum chemistry and urinalysis), as per [Appendix B – Clinical Laboratory Assessment](#), will be performed at the end of the study or after withdrawal/dismissal of a subject from the study.

At the end of the study or after withdrawal/dismissal of a subject from the study, a symptom-directed physical exam with the possibility for a full physical exam if deemed necessary by the PI/Sub-Investigator including vital signs (BP, HR, temperature, pulse oximetry and RR) will be conducted unless the subject is lost to follow up.

A follow up phone call will be made about a week ± 3 days after study participants have been discharged from the study i.e., End-of-study. Clinic will make two additional attempts to contact study participants. If all three attempts are unsuccessful, clinic will close the file and will be deemed lost to follow up. If the first attempted phone call is unsuccessful, the second phone call will be attempted 5 ± 3 days from the first phone call. If second attempt to contact study participant via phone is unsuccessful, a registered letter will be sent 5 ± 3 days from the second phone call.

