11.4 Procedures for Reporting Pregnancy

A positive urine pregnancy test or any hCG level ≥ 5 IU/L for females of child-bearing potential and ≥ 8 IU/L for post-menopausal females will be assessed as clinically significant and will result in the immediate dismissal of the subject from the study, unless deemed otherwise by the Investigator. The elevated hCG will be investigated as a potential pregnancy and will be followed up in the same manner as an AE. A confirmatory hCG blood test will be required for any elevated values. If pregnancy is confirmed, any out of range hCG levels will not be considered an adverse event.

Once notified that pregnancy has occurred during the course of the study or within 30 days of study completion, clinic personnel will report the pregnancy within 24 hours of the confirmatory hCG blood test, to the PI/Sub-Investigator, the IRB, and appropriate Sponsor representative. A Pregnancy Notification Form will be completed as per BPSUSA internal Standard Operating Procedures and will be included alongside any pertinent information at the time of pregnancy reporting. The confirmed pregnancy will be followed to birth of the child or elective/spontaneous termination of the pregnancy. Follow up will occur at minimum once every three months (i.e., once per trimester) until the end of the pregnancy (birth, termination, etc.).

Elective termination will not be considered an adverse event, however supporting documentation detailing the outcome of the procedure will be required. Spontaneous

termination of the pregnancy will be considered a Serious Adverse Event and will be followed up accordingly (as per [Section 11.3](#)). Pregnancy will be treated as AEs for this study.

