13.0 PHARMACOKINETIC AND STATISTICAL ANALYSIS

13.1 Pharmacokinetic and Statistical Analysis Data Set

The data from at least one of the following subjects will be included in the PK and statistical analysis:

1. Subjects who complete all study periods.
2. Subjects who have missed samples but for whom it has been predicted prior to the start of bioanalytical analysis that reliable estimates of the PK parameters should be possible.
3. Subjects who drop out from the study but have completed at least 2 periods.

If a subject's pre-dose concentration is less than or equal to 5% of the C_{max} value for that subject in the given period, then the subject's data in that period without any adjustments can be included in all PK measurements and calculations. If the pre-dose value is greater than 5% of the C_{max} , data from that subject in that period will be dropped from the PK and statistical analysis. Data for subjects dropped due to higher than 5% of C_{max} pre-dose concentrations will be included in a separate appendix in the final study report.

For subjects who are dismissed from the study due to non-compliance or any reason other than AEs, other data of non-impacted period(s) for that subject, which fulfills the PK analysis data set requirements, as above, will be included in PK stats analysis. Data does not fulfill the requirements will be presented separately.

If a subject is dismissed/withdrawn due to an AE from a study period, the data from that period will not be included in the PK stats analysis and will be presented separately. All other data for that subject, which fulfills the PK analysis data set requirement, as above, will be included in PK stats analysis. Data does not fulfill the requirements will be presented separately.

Data from other subjects who were dismissed or withdrew due to elevated hCG levels or are confirmed to be pregnant will not be included in the PK and statistical analysis. The data for these subjects will be presented separately.

Any decision for excluding data prior to start of sample bioanalysis (e.g Major protocol deviation) will be provided with a detailed explanation and will be properly recorded and dated.

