APPENDIX A – SCHEDULE OF EVENTS

	Screening	Check -in	Period 1, 2, 3 and 4				Return Visit			EOS
Study Day	-30 to 0	-1	1	2	3	4	5	6	7	Last visit of Period 4
Confinement		X	X	X	X	X [#]				
ICF	X									
Demographics	X									
Medical/Medication History	X									
Physical Exam	X									X
Body weight	X									
Height	X									
BMI	X									
Vital Signs (BP & HR)	X	X	X ^a	X ^b	X ^c	X ^d				X
Safety measures for COVID-19 [#] (Symptom Check, Temperature, Pulse Oximetry and RR)	X	X ^e	X ^e	X ^e	X ^e	X ^e	X	X	X	
SARS-CoV-2 Test (If applicable)		X								
Urine Drug Tests	X	X								
Alcohol Test	X	X								
Pregnancy Test	X*	X*								
12-Lead ECG	X									
Hematology	X	X								X
Serum Chemistry	X	X ^f								X
Urinalysis	X	X								X
Serology (HIV, Hepatitis B and C) Magnesium Creatinine Kinase Lipid panel	X									
Inclusion/Exclusion criteria	X	X ^g								
Compliance check		X					X	X	X	
Randomization			X							
Tacrolimus Capsule Administration			X							
PK Sampling			X ^h	X ^h	X ^h	X ^h	X ^h	X ^h	X ^h	
Questioning subjects if use of any concomitant medication	X	X					X	X	X	
Adverse Events			X	X	X	X	X	X	X	
Meals		X	X	X	X	X				

* Serum pregnancy test at screening and urine pregnancy test at each period check-in.

Study exit at 72 hours post-dose tacrolimus

a: 1, 2, 4, 6- and 12-hours post-dose

b: 24hours post-dose

c: 48 hours post-dose

d: 72 hours post-dose

e: At pre-dose, at 6- and 12-hours post-dose and then at every 12 hours until discharge at each study period.

f: At check-in period 1 and 3.

g: Only at check-in for the period 1

h: Pre-dose (0 hour) and at 0.25, 0.50, 0.75, 1.00, 1.25, 1.50, 1.75, 2.00, 2.25, 2.50, 2.75, 3.00, 3.50, 4.00, 5.00, 6.00, 8.00, 10.00, 12.00, 16.000, 24.000, 36.00, 48.00, 72.00, 96.00, 120.00 and 144.00 hours after study drug dosing in each study period

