APPENDIX B – CLINICAL LABORATORY ASSESSMENT

TYPE OF TEST	COMPONENTS			
Hematology⁴	
 • Hemoglobin • Hematocrit 	
 • RBC • Platelet count 	
 • WBC and automated differential 	
Serum⁵ Chemistry	
 • Glucose • Calcium • Sodium • Chloride • Bicarbonate (Total CO₂) 	
 • Albumin • Protein • Bilirubin 	
 • AST • ALT • Potassium • Alkaline Phosphatase 	
 • BUN • Urea • Uric Acid • Creatinine
Urinalysis	
 • Bilirubin • Blood • Glucose 	
 • pH • Ketones • Leukocytes 	
 • Nitrites • Protein 	
 • Specific Gravity
Additional Tests	Serology (HIV, Hepatitis B surface antigen, Hepatitis C antibody) ⁶ Magnesium ⁶ Creatine Kinase ⁶ Lipid panel ⁶		Alcohol test Serum hCG (only females, at Screening) Urine hCG (only females, at each period check-in)	
Urine Tests for Drugs of Abuse	Marijuana, Amphetamines, Phencyclidine, Barbiturates, Cocaine, Opiates, Benzodiazepines			

⁴ At Screening, at each check-in and at EOS

⁵ At screening, at check-in for period 1 and 3 and at EOS

⁶ At screening only

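### No pregnancy test is scheduled after a woman's last dose; adding urine hCG to the end-of-study urine sample is a cheap improvement (minor)

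*Combined protocol and SAP*

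**What the plan says.** The hCG schedule appears in four places, and they agree.

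- Section 2.0, footnote to the pregnancy row: "Serum pregnancy test at screening and urine pregnancy test at each period check-in". The row is blank in the Post-Study/EOS column.
- Section 5.1.2.1: urine hCG for all female subjects at each period check-in.
- Appendix A: pregnancy test marked at screening and check-in only.
- Appendix B: "Urine hCG (only females, at each period check-in", with serum hCG at screening.

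The post-study panel in Section 5.1.3 is "Clinical laboratory tests (hematology, serum chemistry and urinalysis), as per" Appendix B, done at end of study or after withdrawal or dismissal. It contains urinalysis but not hCG. For subjects who withdraw or are dismissed, Section 7.6 says that post-study testing is done where possible.

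On timing, Appendix A heads the EOS column "Last visit of Period 4". Section 2.0 adds the footnote "EOS with one-week ±3 days window", and Section 5.1.3 attaches that week and its three-day margin to a follow-up phone call.

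Other routes to detection exist. Section 5.1.2.1 says "Clinical staff reserves the right to conduct random testing", which includes urine hCG at any time during the study. Section 7.2 obliges a woman to report a pregnancy arising up to 30 days after her last dose. Section 2.0 marks adverse-event reporting at EOS, Section 11.3 allows events to be elicited by general questioning, and Section 11.4 states "Pregnancy will be treated as AEs for this study".

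**The concern.** Section 11.4 takes pregnancy seriously. An elevated hCG leads to dismissal and a confirmatory blood test. A confirmed pregnancy is reported within 24 hours and followed to birth or termination. During Periods 1 to 3 a scheduled test can set this in motion after each dose, because the next check-in includes one. After the last dose nothing scheduled does. Self-report and general questioning work only if the woman already knows that she is pregnant, and random testing is a right that staff may or may not use.

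What is at stake is late or missed follow-up of a pregnancy exposed to tacrolimus. The bioequivalence conclusion is not in question.

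**Working it through.** **Inputs.** Four periods, with washout of at least 14 days between doses (Sections 5.1.2.2 and 5.2). Check-in about 24 hours before dosing (Section 5.1.2.1) or at least 12 hours before (Section 5.2), so 0.5 to 1 day. Last sample at 144 hours, which is 6 days. Return visits at 96, 120 and 144 hours. About 64 subjects dosed, at least 48 to complete (Section 7.1).

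**1. Check of the timeline.** With minimum washout the doses fall on days 0, 14, 28 and 42. First check-in to last sample is 3 × 14 + 6 + (0.5 to 1) = 48.5 to 49 days, which agrees with the roughly 50 treatment days in Section 5.2.

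**2. Where EOS falls.** Each period has 1 check-in and 3 return visits, so 4 × (1 + 3) = 16 visits. Section 2.0 numbers everything after screening, EOS column included, as Visits 2 to 17, which is also 16 visits. No number is left for a separate EOS visit. This matches Appendix A, which puts EOS at the last Period 4 visit (144 hours).

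**3. Scheduled tests after each dose.**

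| Dose | Next scheduled hCG test | Days after dose (minimum washout) |
|---|---|---|
| 1, 2, 3 | next period's check-in | 14 − 1 = 13 to 14 − 0.5 = 13.5 |
| 4 | none | – |
| Last dose of a woman who attends no later check-in | none | – |

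**4. Gain from a test at 144 hours.** Let L be the days from conception to a positive urine test. The Period 4 check-in test finds conceptions up to (0.5 to 1) + L days before dose 4. A test at 144 hours finds those up to L − 6 days before dose 4. The difference is 6 + 0.5 = 6.5 to 6 + 1 = 7 days, whatever L is.

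**5. Which pregnancies are added.** The documents give no value for L. For any L above 6 days, the latest conception found at 144 hours lies before dose 4, so each added case was already conceived when dose 4 was given. Taking 10 to 14 days as an assumption:

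- check-in test: up to 0.5 + 10 = 10.5 to 1 + 14 = 15 days before dose 4;
- 144-hour test: up to 10 − 6 = 4 to 14 − 6 = 8 days before dose 4.

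**6. Number of tests.** A woman who completes the study goes from 1 serum + 4 urine = 5 tests to 6. The plan does not say how many women will enrol. If all of about 64 dosed subjects were women of child-bearing potential, the addition would be about 64 urine tests.

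**7. Side effect on the PK set.** Section 13.1 says that data from subjects who "are confirmed to be pregnant will not be included in the PK and statistical analysis". If a positive EOS result removed one completer, the loss would be 1/64 = 1.6% to 1/48 = 2.1% of subjects. With unchanged variance, confidence intervals would widen by about √(64/63) − 1 = 0.8% to √(48/47) − 1 = 1.1%.

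**The case against.** The strongest reply is that this is a design choice and that the plan is internally consistent. Contraception is required until 30 days after the last study procedure (Section 7.2), with a matching duty for women who discontinue (Section 7.6). There are also a reporting duty, adverse-event questioning at EOS, a follow-up call, discretionary testing and extra laboratory samples at the investigator's discretion (Section 8.1.4). No objective of the study fails without the test. A negative result at 144 hours says nothing about conceptions near or after the last dose and could reassure falsely.

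Much of this stands. The expected number of pregnancies found is probably small and cannot be estimated from the documents. Early leavers may not be tested at all, and the documents contain no cost figures. It does not close the gap, because none of the listed routes is a scheduled test.

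Three stronger readings should not be drawn.

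- A reader might take the window footnote in Section 2.0 to mean a separate EOS visit a week or more after the 144-hour sample, with a correspondingly larger gain. The visit count and Appendix A point to the 144-hour visit, and Section 5.1.3 ties the window to a phone call, at which no urine is collected.
- A reader might infer that every early leaver goes untested after her last dose. A woman dismissed at a later check-in is tested there.
- A reader might want Section 13.1 rewritten here to keep every period with a negative check-in test. How that rule treats a pregnancy first found after Period 4 is a separate question that a self-reported pregnancy would raise anyway. Such a retention rule would also keep a Period 4 profile from a woman who, by step 5, was probably already pregnant when dosed.

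**Conclusion.** The gap in the schedule is certain: four places agree, and none lists a test after the last dose. It is minor. The benefit is earlier entry into the Section 11.4 follow-up for pregnancies exposed to the last dose, with the detectable conception date moved 6.5 to 7 days later. No exposure is prevented, and sample size, power and error rates are unaffected apart from the possible loss of a subject in step 7.

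The gain rests on EOS at the 144-hour visit and check-in 12 to 24 hours before dosing. The statement that added cases were already conceived at dose 4 rests on the assumption that a urine test turns positive more than 6 days after conception. Calling the change cheap is a judgement, based on the use of an existing sample and an existing call.

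**What to change.** Add urine hCG for women of child-bearing potential to the EOS/early-termination tests in Section 2.0, Section 5.1.3, Appendix A and Appendix B, run on the urine already collected for urinalysis. For early leavers this applies where possible, as Section 7.6 already provides. Have the follow-up call in Section 5.1.3 ask about pregnancy.

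The cost is one urine test per woman, one question in an existing call, and protocol and consent-form wording. No extra visit or blood draw is needed unless a result is positive. There are three downsides:

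- occasional false positives will need the confirmatory blood test in Section 11.4;
- conceptions close to or after the last dose are still missed, so the self-report and contraception duties in Sections 7.2 and 7.6 must stay;
- a confirmed pregnancy could take a completer out of the PK set under Section 13.1.
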